7.1 Criteria for inclusion of subjects

A patient must meet ALL of the criteria listed below in order to participate:

1. To participate in the study, patients must have been treated with peginterferon alfa-2a plus ribavirin or peginterferon alfa-2b plus ribavirin for a minimum of 12 weeks. If a patient has received more than one of these guidelines, the most recent one will be considered.
2. The patient must have a previously documented HCC caused by genotype 1 virus (subtype a or b). Patients with other genotypes or with mixed genotypes will not be able to participate. The HCV RNA result at the screening visit should confirm genotype 1 virus infection and be >10,000 IU/mL.
3. The patient must have a liver biopsy with HCC-compatible histology and no other etiology or evaluation with Fibroscan. In the event of:
 - a. **Absence of cirrhosis.** Biopsies or Fibroscan must have been done within 18 months prior to the screening visit.
 - b. **Cirrhosis** No specific time frame is required.
4. All patients with cirrhosis should have an ultrasound scan performed within 6 months prior to the screening visit.
5. Patients must be receiving stable antiretroviral therapy with a CD4 lymphocyte count greater than 100/mm³ and an undetectable HIV plasma viral load (< 50 copies/mL) for more than 6 months. Antiretroviral therapy should contain raltegravir (at least for the past 6 weeks).
6. The patient must be 18 years of age or older.
7. HIV treatment should not contain EFV, NVP, ddI, d4T, AZT, or HIV protease inhibitors.
8. The patient should weigh between 40 and 125 kg.
9. The patient and partner must commit to acceptable contraception from at least 2 weeks prior to Day 1 and until at least 6 months after the last dose of study drug. (negative pregnancy test in women of childbearing potential) (Postmenopause is defined as the absence of menstruation during the year prior to study entry.)
10. Patients must be willing to give written informed consent and, in the opinion of the investigator, be able to follow the protocol visit design.

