8.1 Treatment branches

An open-label, single-arm, multicenter study to evaluate the safety and efficacy of a regimen with boceprevir in polytherapy with peginterferon alfa-2b 1.5 µg/kg or peginterferon alfa-2a 180 µg/kg once weekly subcutaneously (s.c.) and oral ribavirin in adult patients with controlled HIV coinfection in whom prior treatment of chronic hepatitis C with peginterferon and ribavirin has failed.

Since early response to peginterferon (PEG-IFN) and ribavirin (RVB) at week 4 is predictive of response to treatment, either SVR or null response (high negative predictive value: 96%), the duration of response-guided treatment with BOC will depend on the response in ST4, ST8, and ST12.

Patients who achieve a reduction in HCV RNA viral load greater than or equal to one logarithmic unit at week 4 (after the bitherapy phase) will then undergo triple therapy for 32 weeks. If HCV RNA is undetectable at week 8, they will end the tto after 32 weeks of triple therapy and will be followed for another 24 weeks. If HCV RNA is detectable at week 8, at the end of the 32 weeks of triple therapy, patients will receive dual therapy with pegylated interferon and ribavirin for an additional 12 weeks and then follow up for 24 weeks.

Patients who do not achieve a decrease in HCV RNA viral load greater than one logarithmic unit at week 4 after the initial phase of bitherapy (or those who have grade 4 fibrosis - cirrhosis) will receive triple therapy for 44 weeks and will be followed for an additional 24 weeks.

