Grade 4 (<500)	Study weeks 1 and 2: defer or discontinue administration until grade 2 is reached, then resume administration with dose reduction of DOS* levels. Study weeks 3 to 48: defer or discontinue administration until grade 2 is reached, then resume administration with a dose reduction of ONE level. Administer G-CSF at the discretion of the centre's investigator. If neutropenia disappears, the dose may be increased at the discretion of the center investigator.

* The dose reduction levels of PEG-IFN are indicated in the label.

Treatment of IFN-associated thrombocytopenia

Table 2. Treatment of toxicity: decreased platelet count

Platelet count (cells/mm3)	MEASURE
Grade 2 (50,000-99,999)	No
Grade 3 (25,000-49,999)	Halving the dose of interferon
Grade 4 (<25,000)	Suspend the PEG-IFN definitively.

* The dose reduction levels of PEG-IFN are indicated in the label.

Dose reduction of PEG-IFN

Dose reductions should be uniform between participating centers and patients. For this purpose, the following reductions shall be used:

Table 3. Guidelines for Recommended Dose Reduction of PEG-IFN 1.5 µg/kg

		Reduction of one level (decrease to 1.0 µg/kg)			Two-level reduction (decrease to 0.5 µg/kg)		
		Volume			Volume		
Weight at Sit Up*		Pen Size	Injection (ml)	Dosage (µg)	Pen Size	Injection (ml)	Dosage (µg)
40 to 50 kg	88 to 110 lbs	Redipen 50	0,45	45	Redipen 50	0,30	30
>50 to 60 kg	>110 to 132 lbs	Redipen 80	0,35	56	Redipen 50	0,30	30
>60 to 65 kg	>132 to 143 lbs	Redipen 80	0,40	64	Redipen 50	0,35	35
>65 to 75 kg	>143 to 165 lbs	Redipen 80	0,45	72	Redipen 50	0,35	35
>75 to 80 kg	>165 to 176 lbs	Redipen 80	0,5	80	Redipen 50	0,40	40
>80 to 85 kg	>176 to 187 lbs	Redipen 120	0,35	84	Redipen 50	0,40	40

>85 to 95 kg	>187 to 209 lbs	Redipen 120	0,40	96	Redipen 50	0,50	50
>95 to 105 kg	>209 to 231 lbs	Redipen 150	0,35	105	Redipen 50	0,50	50
>105 to 125 kg	>231 to 275 lbs	Redipen 150	0,35	105	Redipen 50	0,50	50

* Use the usual rounding methods: values between 0.1 and 0.4 kg should be rounded down and those between 0.5 and 0.9 kg should be rounded up.

Missed or deferred doses of PEG-IFN

If a dose of PEG-IFN is delayed but is finally administered, the following guidelines are recommended for the following scheduled doses:

- Dose delay of 1 or 2 days: administer on the usual day of administration of the week (for example, if Monday is the usual day of administration and the dose is delayed to Wednesday, the next dose will be administered as usual, on Monday).

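### For peginterferon alfa-2b, the half dose ordered for grade 3 thrombocytopenia matches neither level of the protocol's own dose-reduction table

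*Combined protocol and SAP*

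**What the plan says.** Section 8.1 sets the alfa-2b starting dose: "peginterferon alfa-2b 1.5 µg/kg" once weekly. Alfa-2a is the permitted alternative.

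Section 10.3 then gives four pieces of guidance that bear on a fall in platelets.

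- Table 2, grade 3 (25,000-49,999/mm³): "Halving the dose of interferon". At grade 4, peginterferon is stopped for good.
- A footnote under Table 2 refers to the label for the reduction levels.
- The paragraph after it says "Dose reductions should be uniform between participating centers and patients", and then "For this purpose, the following reductions shall be used". Table 3 follows, titled "Guidelines for Recommended Dose Reduction of PEG-IFN 1.5 µg/kg". Its two dose columns are headed "Reduction of one level (decrease to 1.0 µg/kg" and "Two-level reduction (decrease to 0.5 µg/kg" (closing brackets left off).
- A separate table later in the section covers alfa-2a. For platelets between 25,000 and 50,000/mm³ it lists 135/90/45 µg without saying which of the three applies.

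Table 1, on neutropenia, expresses its reductions as one or two levels, which can be looked up directly in Table 3. Table 2 gives a fraction and names no level.

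**The concern.** A centre treating an alfa-2b patient with grade 3 thrombocytopenia has three sources: a fraction in Table 2, a pair of levels in Table 3, and the label. Within the protocol, the fraction and the levels do not agree. Reasonable investigators could settle on level one, level two, or a half dose worked out by hand.

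Uniform reduction across centres, which the section sets as its own aim, would then be lost for this toxicity. Safety is part of the primary objective. The section describes platelet falls as usually dose-dependent, and grade 3 is the last step before permanent loss of peginterferon, which also ends ribavirin and boceprevir. The dose given at this point therefore bears on both tolerability and the chance of completing treatment.

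**Working it through.** **Inputs.** Starting dose 1.5 µg/kg (section 8.1 and the title of Table 3). Reduction levels 1.0 and 0.5 µg/kg and the doses by weight band (Table 3). Platelet rule: half (Table 2). Alfa-2a full dose 180 µg (section 4.1; section 8.1 prints the unit per kg, a separate discrepancy) and steps 135/90/45 µg (section 10.3).

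**Step 1. Half dose against the nominal levels.** Half dose = 1.5 / 2 = 0.75 µg/kg.

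| Instruction | µg/kg | Share of 1.5 | Relative to half dose |
|---|---|---|---|
| Table 3, one level | 1.0 | 1.0/1.5 = 66.7% | 1.0/0.75 = 1.33 (33% above) |
| Table 2, half | 0.75 | 50% | 1.00 |
| Table 3, two levels | 0.5 | 0.5/1.5 = 33.3% | 0.5/0.75 = 0.67 (33% below) |

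The half dose lies exactly midway between the levels, so rounding to the nearest level does not settle the matter. The highest and lowest candidates differ by 1.0/0.5 = 2-fold.

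**Step 2. The doses printed in Table 3.** Half dose in µg = 0.75 × weight.

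| Weight band | Half dose (µg) | One level (µg) | Two levels (µg) |
|---|---|---|---|
| 40-50 kg | 30.0-37.5 | 45 | 30 |
| >65-75 kg | 48.75-56.25 | 72 | 35 |
| >105-125 kg | 78.75-93.75 | 105 | 50 |

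At 70 kg the half dose is 52.5 µg, against entries of 72 and 35 µg. In all nine bands the half dose falls between the two entries. The one coincidence is a patient of exactly 40 kg, for whom 30 µg is half of 60 µg.

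**Step 3. Patients already reduced.** For a patient already at 1.0 µg/kg, half of the current dose is 0.5, which is level two; half of the starting dose would still be 0.75. Table 2 does not say which dose is to be halved. This case does not create a half-dose level for a patient on full dose.

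**Step 4. Alfa-2a.** 135/180 = 75%, 90/180 = 50%, 45/180 = 25%. A half-dose step exists, so the arithmetic conflict does not arise, but the row does not say that 90 µg is the step that answers to Table 2.

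**The case against.** The strongest reply is that Table 2 deliberately gives a fraction and Table 3 only serves rules written in levels, as Table 1 is. On that reading the platelet rule stands alone. It is a possible reading, but the text placed directly after Table 2 says the listed reductions are the ones to use, without excepting platelets. The fair description is conflicting guidance, not an instruction that is impossible to follow.

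Two qualifications stand. The status of Table 3 is mixed: its lead-in is binding in tone, while its title speaks of recommended guidelines, so a reader who infers that the table is mandatory goes further than the text allows. And the label may contain a half-dose step; the technical data sheets are in Annex I and are not available here. That pointer adds a third source and does not reconcile the protocol's own two tables.

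A reader might also infer that the second-level column is wrong at the extremes of weight. The arithmetic is right: 30 µg is 30/50 = 0.60 to 30/40 = 0.75 µg/kg at 40-50 kg, and 50 µg is 50/125 = 0.40 to 50/105 = 0.48 µg/kg in the top band. Both bands can be enrolled ("The patient should weigh between 40 and 125 kg"). But each band prints one pen, one volume and one dose, so centres have nothing to choose between. Fixed doses over bands of 5 to 20 kg must drift around a nominal figure. Other bands also never reach 0.5: >60-65 kg gives 35/65 = 0.54 to 35/60 = 0.58. This is plausibly banding by pen volume. At most, the column headings should be read as nominal.

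**Conclusion.** The point holds as an internal inconsistency in section 10.3, for peginterferon alfa-2b only. Table 2 calls for 0.75 µg/kg from a full dose of 1.5; Table 3 offers 1.0 or 0.5 µg/kg; nothing in the protocol links the two. The plausible doses for one platelet count span a factor of two. This assumes a patient on the full starting dose and takes the Table 3 headings as nominal.

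A reader might infer that the inconsistency affects all peginterferon in the trial, or that it biases the SVR estimate by some stated amount. The documents support neither. Alfa-2a has its own platelet row with a half-dose step. The documents give no grade 3 platelet rate, no alfa-2b/alfa-2a split and no weight distribution, so neither the number of patients affected nor any effect on SVR can be calculated. The trial has a single arm, so no comparison between arms is at risk, and the sample size calculation is untouched. What remains is avoidable variation between centres in interferon exposure at a point that matters for safety.

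**What to change.** Reconcile Table 2, Table 3 and the label footnote so that the platelet rule and the reduction table give one instruction for alfa-2b: state which reduction Table 2 means, in the same terms as Table 3, and whether it applies to the starting or the current dose. Say which source governs if the label differs. State which step of the alfa-2a platelet row (135/90/45 µg) corresponds to the Table 2 rule. If Table 3 is to be binding, align its title with its lead-in; a note that its µg/kg headings are nominal would be enough for the weight bands.

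The sponsor decides the doses; no dose is proposed here. The cost is an amendment to protocol wording, with no change to sample size, endpoints or analysis.

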10.4 COMMUNICATION TO RESEARCHERS

The sponsor shall communicate to investigators any information that may affect the safety of the trial subjects as soon as possible.

It is advisable when deemed appropriate that information on serious and unexpected adverse reactions (RAGI) be presented in a list together with a brief analysis of the data provided.

Researchers must also be informed of the safety aspects that impact the conduct of the clinical trial or the development of the product. Including disruption of the development program or security-related protocol modifications.

Follow-up of subjects after adverse events will be performed by clinical and complementary examinations necessary for the duration of treatment and then on a monthly basis during follow-up and up to 30 days after the end of treatment. In the event of a possible pregnancy, the health status of both the mother and the newborn will be monitored during the trial, whether the person who has become pregnant is the one who is taking the investigational drug or if it has been taken by her partner.

No interim analyses are planned for the present study.

11. Statistics

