4.3 Treatment Regimen

PEG-IFN alfa-2a or 2b and ribavirin will be provided by each hospital and will be administered in accordance with the approved technical data sheets.

BOC (Boceprevir). Provided by the study sponsor.

Description:

BOC is supplied in 200 mg capsules. Each capsule contains 200 mg of BOC, sodium lauryl sulfate, microcrystalline cellulose, lactose monohydrate, croscarmellose sodium, pregelatinized starch, and magnesium stearate packaged in number 0 hard gelatin capsules. Each capsule contains approximately 56 mg of lactose monohydrate. In people with lactase deficiency, the clinical manifestations of lactose intolerance require 3 to 5 g of lactose (4 to 7 times the total amount of BOC capsules) to appear.

Route of administration: oral

Dosage: total daily 2400 mg, (12 capsules).

Storage: keep in the fridge at a temperature between 2°C and 8°C. The products of the study must be stored in a safe place with limited access and in the storage conditions specified on the supply label.

[figure not shown]
Dosage Schedule:

Boceprevir is administered three times a day using a dosing schedule of 4 capsules every 8 hours. Actual times of dose administration may be modified to fit the patient's schedule, although 7- to 9-hour

intervals between administrations should be maintained. All doses of boceprevir will be given with food (a small snack is sufficient).

Study period and treatment:

All patients will receive an initial 4 weeks of bitherapy with Peg-Interferon and ribavirin (PR).
-If there is a decrease in HCV RNA greater than 1 logarithm with respect to baseline HCV-RNA, the patient will be included in the treatment scheme detailed below.

-If the RNA drop is ≤ 1 log at week 4, PR/boceprevir will be administered for an additional 44 weeks. All cirrhotic patients will receive PR for 4 weeks, followed by RP/boceprevir for another 44 weeks

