Adverse reaction (AR) is any harmful, unintended reaction to an investigational drug, regardless of the dose administered. In this case, there is a suspicion of a causal relationship between the investigational drug and the adverse event.

Serious adverse event (SAE) is any adverse event that, at any dose, results in death, threatens the life of the subject, makes hospitalization necessary or prolonged hospitalization, results in permanent or significant disability or disability, or results in a congenital anomaly or malformation. For the purposes of notification, suspected adverse events that are considered medically significant, even if they do not meet the above criteria, will also be treated as serious, including major medical events that require intervention to prevent one of the consequences described above from occurring. Likewise, all suspected transmission of an infectious agent through a drug will be reported as serious. Examples of these events include allergic bronchospasm requiring intensive treatment in an emergency department or at the individual's home, blood dyscrasia or seizures that do not require hospitalization, or the development of drug dependence or abuse.

Medical and scientific judgement should be used to decide whether other situations that have not resulted in the outcomes listed in the above definitions should be reported as SAGs.

A life-threatening term is defined as a situation where, in the opinion of the physician, the patient at the time of the adverse event or adverse reaction is at real risk of death.

Hospitalization or prolongation of a hospitalization is a criterion for considering an AA to be serious. Only admission in which the patient spends the night in the hospital should be considered as hospitalization. The following situations will not meet the AAG criteria:

- if hospitalization or prolongation of hospitalization is necessary to perform a procedure required by the protocol (for example, if day or night visits will be made for biopsies or surgeries required by the protocol).
- if hospitalization or prolongation of hospitalization is part of the facility's routine procedure (e.g., removal of a stent after surgery)
- in case of scheduled hospitalization for a pre-existing process that has not worsened (e.g. scheduled hospitalization for the implantation of a knee prosthesis for a previous osteoarthritis process)

Grade IV laboratory alterations will be considered AAG.

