10.2. Notification

The investigator or designee **must notify all AAGs, regardless of whether or not they are considered drug-related or planned**, to the CTU manager. [name] ([contact]) [contact] [name] and [contact] in order to notify local and national health authorities **within one working day of becoming aware of the event**, so that the contact of the designated promoter can prepare the corresponding written report. AAGs occurring will be reported at any time from the subject's inclusion in the study and up to 30 days after the study has been completed or discontinued. In the specific case of selection failure, the AAGs will be recorded from the moment the consent is signed until the subject is considered a selection failure.

Regardless of the classification of adverse effects, the Investigator must collect all the AEs in the corresponding section of the study data collection notebook (CRD) and fill in all the information pertaining to them.

The sponsor must notify in an EXPEDITIOUS manner all relevant SAFETY INFORMATION, i.e. that could modify the risk/benefit ratio of the investigational medicinal product, or determine changes in its administration schedule or in the conduct of the trial, for example:

- a qualitative change or an increase in the percentage of occurrence of expected RAGs, which is considered clinically important.
- RAGIs that occur after the completion of a clinical trial and that are notified by the investigator to the sponsor.
- New developments related to the conduct of the trial or the development of the investigational medicinal product and likely to affect the safety of the subjects, such as:
 - Serious adverse events that may be associated with the trial procedures and may modify the conduct of the trial
 - A significant risk to subjects such as the lack of efficacy of an investigational drug used for the treatment of a life-threatening disease.
 - Important new safety findings from new animal studies (such as cardiogenicity).
 - Any premature termination or temporary halt of a clinical trial with the same investigational medicinal product for safety reasons, carried out in another country and by the same sponsor.
 - GRAs related only to an MNI that are considered relevant as they are not subject to RAGI's general rules of expedited reporting of individual cases.
- Any recommendations from the data monitoring committee, which are relevant to the safety of the subjects.

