- Dose delay of 3 to 5 days: Giving subsequent doses every 5 to 6 days until the patient gets back to their original schedule (for example, if Monday is the usual day of administration and the dose is delayed until Saturday, the next dose will be given on Thursday, the next dose on Tuesday, and the next dose on Monday).
- 6-day dose delay: discontinue that week's dose and continue with the usual schedule the following week (e.g. if Monday is the usual day of administration but the dose is delayed until the following Sunday, the dose is considered to have been interrupted and the next injection will coincide with the following week's dose, on Monday).
- Dose delay of 7 or more days: The investigator may resume administration of the study drug at any time up to 28 days after the last dose and, if necessary, administer the dose every 5 or 6 days until the weekly dose is received on the patient's usual scheduled day.

Treating the Side Effects of RBV

The most common AA in RBV treatment is anemia, which may be due to hemolysis or decreased release of red blood cells from the bone marrow. Anemia usually appears 1 to 2 weeks after you start receiving RBV and usually goes away within 4 to 8 weeks of withdrawal or reduction of the drug's dose. In patients with anemia secondary to RBV-induced hemolysis, an elevation of indirect bilirubin is common. BOC may increase the incidence or severity of anemia. In case of anaemia during treatment with BOC and RBV, the dose adjustment of RBV, as described below, takes precedence over BOC.

NOTE: A serious side effect of RBV is its teratogenicity; therefore, it is recommended not to administer RBV to pregnant or breastfeeding women and to men whose partner is pregnant. Women who become pregnant during the study will be required to discontinue study treatment and undergo withdrawal assessments.

The dose of RBV in this study will depend on weight at study entry (see section 5). The following table shows the recommendations for dose reduction in case of anemia. The administration of epoetin (EPO) will be at the discretion of the centre's researcher. If the administration of RBV is temporarily or permanently stopped, patients may continue to receive PEG-IFN and BOC.

Board. Recommended RBV dose reduction in anaemia

	Starting dose	Measure
--	---------------	---------

Hemoglobin <10 g/dL, ≥8.0 g/dL.	1,400 mg/day 1,200 mg/day	Decrease RBV to 1,000 mg/day
	1,000 mg/day	Decrease RBV to 800 mg/day

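### Newborn monitoring that ends with the trial, and serious-event reporting that ends 30 days after it, would miss term births from many conceptions in the period when contraception is required

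*Combined protocol and SAP*

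**What the plan says.** - **Risk.** Section 10.3, on ribavirin: "A serious side effect of RBV is its teratogenicity".
- **Precaution.** Section 7.1, item 9, commits patient and partner to contraception "until at least 6 months after the last dose of study drug".
- **Classification.** Section 10.1 includes among serious adverse events one that "results in a congenital anomaly or malformation".
- **Pregnancy follow-up.** Section 10.4: "the health status of both the mother and the newborn will be monitored during the trial". This applies whether the patient or the patient's partner is pregnant.
- **Serious-event reporting.** Section 10.2 runs from inclusion "up to 30 days after the study has been completed or discontinued".
- **Adverse-event follow-up.** Section 10.4 uses a different limit: "on a monthly basis during follow-up and up to 30 days after the end of treatment".
- **Pregnant participants.** Section 10.3 has them stop study treatment and undergo withdrawal assessments.
- **End of trial.** Sections 6.7 and 11.4 place it at the last visit of the last subject recruited.

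**The concern.** The protocol treats a congenital anomaly as a reportable serious event and says it will monitor the newborn. A newborn can be assessed only after birth, and gestation is longer than the 24 weeks of post-treatment follow-up plus 30 days. If birth comes after both limits, nothing in the text shown obliges the investigator to find out the outcome or report it. The trial could then record no anomalies partly because some births came too late to be collected. Pregnancies should be few, so each unrecorded outcome is a large share of what could be learned.

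**Working it through.** **Inputs from the protocol.** Lead-in of 4 weeks (4.3: "All patients will receive an initial 4 weeks of bitherapy"). Longest course (8.1): such patients "will receive triple therapy for 44 weeks and will be followed for an additional 24 weeks". Reporting limit of 30 days after the study (10.2). Contraception for 6 months, taken as 180 to 184 days and about 183. Recruitment of 12 months (1.15, 1.16) or 2 months (6.5).

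**Assumptions not in the documents.** Birth 36 to 40 weeks (252 to 280 days) after conception, with 38 weeks where one value is used. A participant's pregnancy is detected, and treatment stopped, 2 to 8 weeks after conception.

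**1. The plan's own duration.** 4 + 44 + 24 = 72 weeks and 4 + 32 + 12 + 24 = 72 weeks, matching the stated maximum of 72. The shortest course gives 4 + 32 + 24 = 60 weeks.

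**2. A completer's own window, in days after the last dose.**
- Last visit: 24 × 7 = 168. Reporting limit: 168 + 30 = 198.
- Latest conception with birth by day 198: 198 − 252 = −54 to 198 − 280 = −82, that is 7.7 to 11.7 weeks before the last dose.
- Conception on the last-dose day: birth at day 252 to 280, which is 54 to 82 days after the limit.
- Conception at the end of the contraception period: birth at 183 + 252 = 435 to 183 + 280 = 463, which is 237 to 265 days after the limit.

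**3. A participant who conceives on treatment,** stops, and completes 24 weeks of follow-up. The limit falls 2 + 24 + 4.3 = 30.3 to 8 + 24 + 4.3 = 36.3 weeks after conception. That is before a birth at 38 weeks. Only the latest detection combined with the earliest birth (36.3 against 36) would just fall inside.

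**4. The whole-trial reading.** With 12-month recruitment and a last subject who completes 72 weeks, the trial ends at week 52 + 72 = 124. For a patient enrolled in week e who has a conception in study week c, birth is in time if e + c + 38 ≤ 124, so c ≤ 86 − e. For a 48-week course, the contraception period ends at about week 48 + 26 = 74.

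| Enrolment week | Conceptions covered to study week |
|---|---|
| 0 | 86 |
| 12 | 74 |
| 26 | 60 |
| 38 | 48 |
| 52 | 34 |

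On a 48-week course, patients enrolled after week 12 lose part of the contraception period, and those enrolled after week 38 also lose part of treatment. Adding 30 days (4.3 weeks) moves the last enrollee's limit from week 34 to about week 38.

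With the 2-month recruitment in 6.5, the trial ends at about day 61 + 504 = 565. For the first enrollee, conception at the end of a 48-week course gives birth at day 336 + 266 = 602. That is outside even with 30 days added (595).

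**5. The two 30-day limits.** For a completer, 10.4 read literally ends adverse-event follow-up at day 30 after treatment, while 10.2 ends serious-event reporting at day 198. The difference is 168 days. The sentence in 10.4 also provides for monthly checks during follow-up, and follow-up runs well past day 30.

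**The case against.** **The trial is not one patient's participation.** Section 10.4 refers to the trial, and 6.7 and 11.4 define its end by the last subject. On that reading, with 12-month recruitment, every patient is covered for conceptions to about study week 34, and earlier enrollees for longer. This stands and narrows the gap. It does not close it, and the text does not say which reading applies.

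**A reader might infer that the contraception period outlasts the reporting window.** For completers it does not. It ends at day 180 to 184, which is 14 to 18 days before day 198. It passes the 24-week visit by a literal 12 to 16 days, but Section 1.16 describes the same follow-up as 6 months. The shortfall comes from gestation.

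**A reader might infer that the rules cannot observe the outcome at all.** They can in part. For the partner of a man on a 48-week course, a conception up to about week 48 − 11.7 = 36 to 48 − 7.7 = 40 leads to birth within his own reporting window. Early births, losses and anomalies found before birth may also fall inside.

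**A reader might infer that stopping treatment starts the 30-day clock, which would close it 6 to 12 weeks after conception.** The documents do not say so. Sections 7.3 and 10.3 stop treatment, whereas 10.2 counts from the end of the study. Newborn monitoring in 10.4 also presupposes later observation.

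**Section 10.2 covers some post-trial events.** The sponsor expedites unexpected serious reactions that an investigator notifies after completion. This sets no active collection, and a named ribavirin effect may not count as unexpected.

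**Some material is not shown.** The reporting form and the list of data variables are annexes, and the visit tables shown stop at the end of treatment. It cannot be said that follow-up visits omit a pregnancy question.

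**Conclusion.** The point holds as a gap in safety collection. Followed as written, the rules do not secure the outcome of pregnancies conceived late in treatment or after it. On the patient's own window, every term birth from a conception in the post-treatment contraception period falls outside, by 54 to 265 days beyond the reporting limit. On the whole-trial reading with 12-month recruitment, the loss is confined to late-treatment and post-treatment conceptions in later enrollees. The sizes rest on 36 to 40 weeks to birth, on detection at 2 to 8 weeks for pregnant participants, and on a last subject who completes 72 weeks. The direction does not depend on the exact values, because 24 weeks plus 30 days (28.3 weeks) is shorter than any term gestation in that range. The sample size and the virologic response analysis are unaffected.

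**What to change.** 1. In Section 10.4, replace the limit to the trial's duration with follow-up to pregnancy outcome and newborn status, for every pregnancy of a patient or partner conceived from Day 1 to the end of the 6-month contraception period.
2. In Section 10.2, state that congenital anomalies in these pregnancies are notified regardless of the 30-day limit.
3. Reconcile the 30-day limit in 10.4, counted from the end of treatment, with that in 10.2, counted from the end of the study.

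Reaching birth for the latest such conception takes collection to about day 435 to 463 after the last dose, against day 198 now. The cost is protocol wording, a few contacts for a small number of pregnancies, and some reports that arrive after the last visit.
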